## 10.1.2. Ratio determination

Operational properties of various allocation ratios for the following assumptions are as follows:

- 1. Total sample size (for safety main study): n=1200 (900 acoziborole and 300 placebo)
- 2. Excess rate (ER) for safety: 1% (acoziborole = 2% of AEs of interest, Placebo = 1%)
- 3. Probability to detect an infrequent AE ( $\leq 1\%$  upper limit of class)
- 4. Probability to detect an infrequent AE (0.5% mid-class)

5. Total sample size for efficacy (TrypSkin exploratory sub-study): n=725 in order to ensure a minimum of 700 evaluable biopsies

6. Binary endpoint for efficacy: success=no tryps detected in punch skin at month 4, failure = at least one tryp-positive result in punch skin at Month 4

7. Probability to detect at least one trypanosome in derma at baseline: 20%

8. No effect of placebo on occurrence of tryps in derma at month 4: failure rate at 4 months=20%

9. Effect of 95% of acoziborole on occurrence of tryps in derma at Month 4 (efficacy): failure rate at Month 4 =  $0.05 \times 0.20 = 0.01$  or 1%

10. Excess rate of success in acoziborole group: 19% (assuming the same efficacy as stage 2 patients)

	Safety			Efficacy (for TrypSkin sub-study)		
Allocation ratio	Sample size for safety	Exact 95% CI limits of ER	Probability to detect an infrequent AE if occurrence rate = 1% (upper limit), = 0.5% (mid-class) and = 0.1% (lower limit of class)	Sample size for efficacy	Exact 95% CI limits of ER Estimate = 20%	Power (chance to detect a difference vs PBO) if acoziborole efficacy is 95%
3:1	PBO = 300 ACO = 900	Lower = -0.92% Upper = +2.41%	Upper: 99.99% Mid: 99.90% Lower: 59.36%	PBO = 175 ACO = 525	Lower = 13.38% Upper = 25.55%	99.99%
2:1	PBO = 400 ACO = 800	Lower = -0.64 Upper = +2.42%	Upper: 99.96% Mid: 98.18% Lower: 55.06%	PBO = 233 ACO = 467	Lower =14.02% Upper = 24.62%	99.99%
3:2	PBO = 480 ACO = 720	Lower = -2.30%* Upper = +0.66%*	Upper: 99.93% Mid: 97.29% Lower: 51.34%	PBO = 280 ACO = 420	Lower = 14.51% Upper = 24.15%	99.99%
1:1	PBO = 600 ACO = 600	Lower = -0.44% Upper = +2.51%	Upper: 99.75% Mid: 95.06% Lower: 45.23%	PBO = 350 ACO = 350	Lower: 14.81% Upper: 23.48%	99.99%

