# Sample size calculation for the TrypSkin exploratory sub-study:

The primary objective is to estimate the prevalence of dermal extravascular T.b. gambiense trypanosomes in a population of seropositive subjects non-confirmed parasitologically. Preliminary results from Guinea, on a limited number of subjects, have shown that all seropositive individuals presenting a positive CATT test in plasma dilution ≥1:4, but nonconfirmed by parasitological examination of blood and lymph, had parasites in skin biopsies (15). Knowing that approximately 25% of the RDT positive subjects non-confirmed parasitologically present a positive CATT test in plasma dilution ≥1:4, it is hypothesized that up to 20-25% of the population of RDT positive subjects non-confirmed parasitologically enrolled in the TrypSkin exploratory sub-study could possibly carry dermal extravascular parasites. Bearing in mind this higher limit of the skin-dwelling trypanosome prevalence, we have estimated the minimum sample size required to be able to evaluate the real prevalence with a satisfactory precision (a narrow confidence interval [CI]). Under the assumption that skin-dwelling trypanosomes could be observed in up to 20-25% of the 1200 subjects, to obtain a 95% CI with a precision of 3%, a minimum of 690 evaluable subjects is required (Table 6). Based on these calculations and taking into account a provision of 5% (35 subjects) to allow for skin samples that are non-analysable, the target number of subjects to be enrolled in the TrypSkin exploratory sub-study is 725.

	Estimated prevalence					
Precision	0.05	0.10	0.15	0.20	0.25	0.30
0.025	300	550	780	980	1160	1300
0.03ª	200	390	540	690	800	900
0.05	80	130	200	245	290	320

CI=confidence interval.

a. Width of 95% CI approximately 0.06 (6%)

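### 725 TrypSkin subjects do not ensure 700 evaluable biopsies: the plan's own 5% provision leaves about 690, and the Month 4 figures in Table 7 allow for no loss to follow-up

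*Protocol*

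**What the plan says.** Protocol 10.1.1 sizes the TrypSkin sub-study on the precision of a prevalence estimate. For 20% prevalence and a 3-point half-width, "a minimum of 690 evaluable subjects is required". It then adds "a provision of 5% (35 subjects) to allow for skin samples that are non-analysable" and concludes that "the target number of subjects to be enrolled in the TrypSkin exploratory sub-study is 725". SAP 2.4.2 repeats 690 and 725.

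Protocol 10.1.2, item 5, gives the size for efficacy as "n=725 in order to ensure a minimum of 700 evaluable biopsies". The efficacy columns of Table 7 use 700 subjects, which is 175 placebo and 525 acoziborole at 3:1, and report power of 99.99%. The endpoint is defined at Month 4: "success=no tryps detected in punch skin at month 4". SAP 2.4.3 lists n=700 in the same place and does not connect it to 725.

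Three other sections bear on how many subjects will have a Month 4 result:
- Protocol 10.8 (Handling of missing data) analyses observed cases, with a sensitivity analysis that counts missing as positive. SAP 5.3.2 does the same.
- Protocol 9.2 says that subjects lost to follow-up are no longer replaced. The reason given is the main safety objective, for which lost subjects stay in the safety set. SAP 2.4.1 still describes replacement, aimed at 1200 completers in the main study.
- Protocol 3.1 and section 8 end participation after a positive parasitological test.

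**The concern.** One enrolment target is tied to two minimum evaluable numbers, 690 and 700. The plan's only stated loss rate supports the first and not the second. Table 7 is built on the second.

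The 5% provision is for skin samples that cannot be analysed. Nothing in the TrypSkin sizing covers subjects who have no Month 4 biopsy, although the Table 7 efficacy endpoint is a Month 4 biopsy result and missing results drop out of the main exploratory analysis. The 175 and 525 therefore assume both less sample failure than 10.1.1 provides for and complete follow-up to Month 4.

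At stake is whether the stated evaluable size, precision and power describe the sub-study that will actually be run, and which figure the clinical study report should use as the planned size.

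**Working it through.** **Inputs.** From Protocol 10.1.1: 690 evaluable, 5% or 35 subjects, 725 enrolled. From Protocol 10.1.2: 700 evaluable, 3:1 allocation as 175 and 525, Month 4 failure rates of 20% (placebo) and 0.05 × 20% = 1% (acoziborole). From SAP 3.1: two-sided 5%. Month 4 attrition in TrypSkin is not given in either document, so the values below are assumptions.

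**1. Reproducing the plan's figures.**
- Precision: n = 1.96² × 0.20 × 0.80 / 0.03² = 683. The plan states 690.
- Enrolment: 690 × 0.05 = 34.5, rounded to 35, and 690 + 35 = 725. This matches. Dividing instead, 690 / 0.95 = 726.3, or 727.
- Power at 175 v 525 for 20% v 1% (normal approximation): 99.99996%. This agrees with the printed 99.99%.

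**2. What 725 delivers.**
- Taking the provision as 35 subjects: 725 − 35 = 690.
- Taking it as 5% of those enrolled: 725 × 0.95 = 688.75, about 689.
- For 700 to remain, only 725 − 700 = 25 may be lost, and 25 / 725 = 3.4%.
- Enrolment needed for 700 at 5% loss: 700 / 0.95 = 736.8, or 737.

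**3. Baseline precision.** Half-width = 1.96 × √(p(1 − p)/n).
- p = 0.20: 2.96 points at 700 and 2.99 at 689.
- p = 0.25: 3.21 points at 700 and 3.23 at 689. The 3-point target is missed at 25% with either number, so that is not caused by the discrepancy.

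**4. Month 4 interval and power.** Evaluable N = 725 × 0.95 × (1 − a), where a is the assumed attrition, split 3:1. The half-width is the simple (Wald) one, 1.96 × √(0.16/n₀ + 0.0099/n₁).

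| Case | Placebo v acoziborole | Half-width, points | Power, normal approx. |
|---|---|---|---|
| Table 7 (700) | 175 v 525 | 5.99 | 99.99996% |
| 5% sample loss only (689) | 172 v 517 | 6.04 | 99.9999% |
| plus 5% attrition (654) | 164 v 491 | 6.18 | 99.9999% |
| plus 10% attrition (620) | 155 v 465 | 6.36 | 99.9997% |
| plus 20% attrition (551) | 138 v 413 | 6.74 | 99.999% |

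Exact Fisher power is also above 99.99% in every row where it was run (172 v 517 and below). The exact limits printed in Table 7 at 3:1 (13.38% to 25.55%) have a half-length of (25.55 − 13.38)/2 = 6.09 points, close to the Wald 5.99. The Wald form is used here only to show the size of the change.

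**5. Lower prevalence.** If placebo positivity were 2% with the same 95% effect, approximate power would be 72% with 700, 71% with 689 and 68% with 620. Prevalence moves the power far more than 11 subjects do.

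**The case against.** The strongest reply is that 725 was never derived from 700. It comes from 690 in Protocol 10.1.1, and 725 − 35 returns 690 exactly. The 700 appears in a section that compares allocation ratios, where it splits cleanly into 175/525 and 350/350. Correcting it changes no conclusion in that section, and the efficacy analysis is exploratory. All of this is fair, and it sets the size of the point. It does not remove the sentence saying that 725 ensures 700, which the stated provision contradicts. Nor can the word biopsies rescue it: two punches are taken per subject per time point, but Table 7 uses the 700 as numbers of subjects.

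It can also be said that Month 4 loss is likely to be small. Protocol 9.2 calls loss to follow-up low after 1.5 years of conduct, and the missing-as-positive analysis checks robustness. That stands as evidence against a large effect. It is a main-study statement without a rate, however, and loss is not zero: Protocol 7.7.1 mentions replacing the first 8 subjects lost.

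Three stronger readings are tempting, and the documents do not support them:
- **That 725 also falls short of 690.** The gap of one subject depends on whether 5% is taken of 690 or of 725. The formula needs only 683.
- **That the sub-study is underpowered or must enrol more.** Under the plan's assumptions neither precision at 20% prevalence nor power is materially affected.
- **That Month 4 attrition is 5%.** No rate is given for TrypSkin, so 164 v 491 is an illustration and not a forecast.

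**Conclusion.** The statement that 725 enrolled ensures 700 evaluable is wrong on the plan's own figures. About 689 to 690 are delivered, which is 10 or 11 fewer (11/700 = 1.6%). The Table 7 efficacy columns rest on the 700 and also leave out any loss between baseline and Month 4.

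The consequence is minor. This is an internal inconsistency and an unstated follow-up assumption. The power conclusion rests on the plan's 20% v 1% assumption and held at every attrition rate tried up to 20%. The conclusion on baseline precision rests on 20% prevalence.

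**What to change.** - In Protocol 10.1.2, item 5, replace the minimum of 700 by about 690, so that it agrees with 10.1.1.
- Base the efficacy columns of Table 7, and the n=700 and matching table in SAP 2.4.3, on that size at most. At 3:1 this is about 172 v 517, with the other ratios split from the same total.
- Add a sentence saying that the 5% covers non-analysable samples only, and that Month 4 numbers will be lower by whatever attrition occurs. If a rate is assumed, state it.
- Bring SAP 2.4.1 into line with Protocol 9.2 on replacement, so that readers do not take replacement as cover for Month 4 losses.

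The cost is a few words and one recalculation. The exact limits widen slightly and the printed power of 99.99% does not change. Enrolment and study procedures are unaffected.

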#### Table 7. Presentation of different allocation ratio scenarios

ACO=acoziborole; AE=adverse events; CI=confidence interval; ER=excess rate; PBO=placebo

\*Not comparable with other allocation ratio due to decimal digits in the number of subjects requiring rounding to the closest entire number.

#### Conclusions:

- The four allocation ratios allow detection, with sufficient probability, of an infrequent AE with an exception for the lower limit of the class (0.1%) of infrequent events. In that case, the larger the sample in the acoziborole group, the better the probability of detection.
- The upper limit of the exact 95% CI of the ER of AEs is similar irrespective of the allocation ratio.
- The lower limit of the exact 95% CI is closer to the estimate (shorter 95% CI) with a balanced (1:1) allocation ratio.
- The power of a test of success rate (success = no trypanosome observed in skin punch sample at Month 4) is excellent irrespective of the allocation ratio if the effect of acoziborole is similar to the efficacy in stage 2 (efficacy ≥95%).
- The advantage of an allocation of 3:1 is to maximise the number of seropositive subjects exposed to acoziborole. There is a small disadvantage in the exact lower limit of the 95% CI (larger CI), but no real advantage in the power of the efficacy test.
- The main disadvantage of the balanced allocation ratio (1:1) is a smaller number of exposed subjects.

## 10.2. Definition of study populations included in the analysis

For the main safety study, the study population that will be used for the analyses is defined as below:

• **Safety set of subjects** (SS) is a modified intent to treat (mITT) set of subjects composed of all randomised subjects who received at least one tablet of IP (placebo or acoziborole).

For the TrypSkin sub-study, the study populations that will be used for the analyses are:

- **Primary set of subjects** for exploratory efficacy analyses is the mITT set composed of subjects, who participate in the TrypSkin sub-study and who receive at least one tablet of IP (placebo or acoziborole).
- Secondary set of subjects for exploratory efficacy analyses is the set of all seropositive subjects who are positive for the presence of trypanosomes by at least one molecular diagnostic test in the skin, blood and/or DBS at baseline.

#### 10.3. Subject disposition

Subject disposition data will be presented for each treatment group and will include:

- Number of subjects who have a positive g-HAT serology test
- Number of subjects randomised to study treatment
- Number of subjects treated
- Number of subjects who complete the study
- Number of subjects who discontinue the study (with the reasons for discontinuation)

#### 10.4. Baseline

At the end of the study, subject characteristics will be presented using descriptive statistics (N, mean, standard deviation [SD], median, inter-quartile range, minimum, maximum) for continuous variables or frequencies and percentages for categorical variables. This information will be presented for the following baseline characteristics for the acoziborole and placebo groups:

- Demographic data
- Medical history
- Clinical examination
- Laboratory assessments
- Karnofsky performance status
- Concomitant medications

#### **10.5.** Treatment compliance

Information regarding the number of subjects who have fully taken the three tablets during the single dose of study treatment and the number of subjects who vomit in the hour following the administration will be presented descriptively.

#### 10.6. Efficacy analysis

Efficacy analysis is only exploratory in nature and will be conducted under the TrypSkin substudy described in section 10.8.

#### 10.7. Safety analysis

#### **10.7.1.** Primary endpoint analysis

Adverse events will be coded using the Medical Dictionary for Regulatory Activities (MedDRA) SOC and PT. Occurrence rates of each TEAE (≥1%), by MedDRA PT, will be compared.

The primary endpoint for this study is the occurrence of TEAEs from administration of study drug to 4 months post-treatment. It is a binary endpoint (presence or absence of any TEAE).

The primary outcome measure is the ER of TEAEs over the first 4 months post-treatment in the acoziborole group compared with placebo. The occurrence rate will be the number of subjects with at least one TEAE as the numerator and the number of subjects who receive at

least one tablet of study medication (the SS) as the denominator. Loss of subjects to follow-up and withdrawal for a reason unrelated to safety or tolerance will not be considered as AEs.

The ER of occurrence of any TEAE will be transformed to the number of subjects needed to treat (NNT) to observe one more subject with a TEAE in the acoziborole group compared with placebo (NNT=1/ER).

The Cochran-Mantel-Haenszel test, stratified by study centre, will be used to compare the occurrence rate of TEAEs between treatment groups. The same test will be applied to the primary endpoint and each component of the composite endpoint (common TEAEs based on PTs).

Generalisability of the treatment effect will be assessed using a test of homogeneity of the odds ratio (OR) across study centres. If the number of randomised subjects in each study centre reaches 100, each study centre will be considered as a stratum. If one or several study centres has fewer than 100 subjects, the smallest study centres will be pooled together to obtain strata of at least 100 subjects. If the test of homogeneity is not significant, the common OR and the 95% CI will be estimated. If the hypothesis of homogeneity is rejected, the OR per study centre will be provided.

Treatment-emergent AEs will be categorised by severity.

All statistics will be provided to ensure that the most pertinent events (serious and severe) are not "lost" amongst non-serious and non-severe events.

Treatment-emergent AEs will also be categorised by period of occurrence during the study. Two successive periods of time will be considered:

- Occurrence during the hospitalisation period
- Occurrence or prevalence after the hospitalisation period (from discharge to Month 4).

The AE can occur in both periods for the same subject (i.e. the event is still present at the second time period). However, for the period analysis the AE start date will be used to identify AEs in each period. The denominator of occurrence rate in each period will respectively be the number of subjects who receive at least one tablet of study treatment during the first time period and the number of subjects attending the 4-month visit or have reported a TEAE during the second time period. All statistics will be provided per time period to separately assess and interpret early events probably attributed to study treatment and late events that could be attributed to the disease or are persistent.

The time course of treatment effect will be analysed using the log rank test stratified by study centre and will be performed on the time to occurrence of TEAEs, taking into account the attrition rate of subjects who are being followed up. A loss to follow-up or a withdrawal will be censored at the time of the last attended visit. The Kaplan-Meier estimates of the proportion of subjects without any TEAE in each treatment group will be presented graphically to assess the time course of the response.

The hierarchy of testing reflects the sequence of testing from the more general effect to the most specific effect. There is a multiplicity of testing issue and an inflation of type I error that cannot be discarded. However, no adjustments of type I error are planned for this study as this study has been designed to detect any potential safety issues rather than confirming and investigating a safety concern.

The rate of occurrence of AEs will be analysed by the true positive status (subjects with parasites detected during the follow up period) in either treatment or placebo groups.

The rate of conversion to parasite positive and the rate of return to seronegative over 4 months will be analysed descriptively using frequency and proportion by treatment group.

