In the 13-week toxicity studies conducted to fully cover the length of time patients are exposed, the pancreas, adrenal gland and epididymis were identified as target organs.

Compared with earlier 28-day toxicity studies, only the spermatic granulomas observed in the epididymis of some rats at 15 and 30 mg/kg was a new finding. Following the administration of acoziborole for 13 weeks, the NOAEL was 5 mg/kg and 20 mg/kg in rats and dogs, respectively.

In conclusion, the rat is the most sensitive species and should be used to estimate the therapeutic index.

In reproductive toxicity and embryotoxicity/fetotoxicity studies, including teratogenicity, acoziborole did not induce any changes in reproduction parameters in males or females, nor any abnormalities in embryos/fetuses in rats and rabbits or in treated parturient mothers, suckling neonates or the post-weaning young.

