#### 3.3. Rationale of study design

The WHO-HAT elimination network recommended that the current study should include a sufficiently large number of subjects treated with acoziborole to reach a 95% probability to detect at least one uncommon AE. According to the sample size calculation, if 900 subjects are exposed to acoziborole, there would be a high chance (>99%) of detecting at least one AE (if the incidence rate is 1%). Therefore, it is planned that 900 subjects will be administered with acoziborole and 300 subjects with placebo, for an overall sample size of 1200 subjects.

[figure not shown]
To avoid any bias in AE/ TEAE collection, the study will be double-blinded and placebocontrolled with an allocation ratio of 3:1 (acoziborole:placebo). For more details about the rationale for the ratio decision, please refer to Section 10.1.2.

Standard safety assessments during this study will be the collection of TEAEs/AEs and laboratory safety parameters.

As the pivotal study (DNDi-OXA-02-HAT) demonstrated that 97.7% of TEAEs related to acoziborole occurred within 5 days after acoziborole administration, subjects will be hospitalised for an observational follow-up period of 5 days and will be asked to come back for on-site follow-up visits at Months 1 and 4. The visit at Month 4 corresponds to clearance of acoziborole as shown by results from the mass balance study (DNDi-OXA-03-HAT study).

Moreover, to ensure a close follow-up of subjects and encourage study adherence, investigator contacts will be established between the site and study subjects at Months 2 and 3. If deemed

necessary by the investigator, an on-site unscheduled visit will be proposed. The overall study design is summarised in Figure 2.

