1.1. Background and rationale

Human African trypanosomiasis (HAT) is a neglected tropical disease, transmitted by the bite of a tsetse fly, affecting sub-Saharan African countries. Without prompt diagnosis and treatment, it is usually fatal. Few treatments are available and, although the treatment options have advanced with the recent approval of fexinidazole, a ten-days oral treatment for the parasitologically confirmed g-HAT cases, there are still gaps with regards to management of the challenges of integrated treatment not only of confirmed but also the suspects individuals when foreseeing the 2030 Public Health objective of sustained HAT elimination.

Whilst the delivery of fexinidazole has improved the management of g-HAT cases and facilitated the integration of HAT treatment into the general health system, it is expected that the current investment in acoziborole will help boost such integration and the elimination efforts.

In the single ascending dose study in healthy volunteers (randomized, double-blind, placebocontrolled study), acoziborole was well tolerated and the following pharmacological parameters were observed³:

- Tmax around 72h, stable for at least 4 days
- Long half live (T1/2 of about 400h) allowing single administration.
- Low metabolite detection
- Low inter-subject variability
- Unbound fraction around 2.2%
- Adverse events observed were not dose dependent.

Acoziborole as an oral, single-dose treatment envisioned for all stages of g-HAT, was studied in an open-label pivotal Phase II/III trial (DNDi-OXA-02-HAT) in DRC and Guinea. The safety and efficacy results from the pivotal study have provided data that envision the treatment of parasitologically confirmed g-HAT cases.

The standard g-HAT case definition implies the demonstration of the parasite in any body fluid via microscopy. However, there are factors such as low parasitemia and the complexity and low sensitivity of parasitological methods that make such demonstration difficult. It is known that

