5.1. Primary Objective Analysis

The assessment of the safety of a single dose of acoziborole compared to placebo during a follow up period of 4 months will be conducted using excess rate (ER) of occurrence of any TEAE over the first 4 months in the acoziborole group compared to placebo. The numerator of the occurrence rate will be the number of subjects with at least one TEAE and the denominator will be the number of subjects in the Safety Set. In addition, a sensitivity analysis will be performed on safety set population excluding subjects with treatment misallocation. The ER is the occurrence rate of any TEAE in the acoziborole group minus the occurrence rate in the placebo group. The 95% confidence interval (CI) of the excess rate will be calculated using Wilson score interval (which provides average coverage very close to 95% in all cases⁹). The excess rate (ER) of occurrence of any TEAE will be transformed to the number of subjects needed to treat (NNT) to observe one more subject with a TEAE in the acoziborole group compared to placebo (NNT = 1 / ER).

The analysis will be performed on the total SS population and by age groups (defined as adolescents aged 15-17 years and adults aged \geq 18 years), gender, TEAE severity category and period of occurrence. Four categorizations of TEAEs per severity will be derived as 1) Serious AEs regardless of the relationship to drug, 2) severe and related to drug TEAEs and 3) mild and/or moderate regardless of relationship to drug, and 4) severe but not related to drug. TEAEs period of occurrence will be categorized as: 1) Occurrence during the hospitalization period and 2) Occurrence after the hospitalization period (from EoH to month 4). The same event for the same subject can occur at both periods (i.e., the event is still present at the second period). However, for the analysis the AE start date will be used to identify AEs in each period. The denominator of occurrence rates will be the number of subjects receiving at least one tablet of IP for the first period and the number of subjects attending the 4-month visit or having reported a TEAE during the second period.

The occurrence rate analysis will be performed on a safety set. MedDRA preferred terms of TEAE with occurrence rates ≥1% in one treatment group will be compared between treatment groups on the excess rates and NNT for any TEAE, by TEAE severity to assess whether the more severe

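### The single discharge-to-Month-4 window pools the weeks of highest remaining acoziborole exposure with later months, and the protocol's advance reading of late TEAEs sits badly with the documents' own PK

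*Protocol*

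**What the plan says.** Protocol 10.7.1 defines two TEAE periods: the hospital stay, and "Occurrence or prevalence after the hospitalisation period (from discharge to Month 4" (the bracket closes there). Events go to a period by AE start date. The stated purpose is to "separately assess and interpret early events probably attributed to study treatment and late events that could be attributed to the disease or are persistent".

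SAP 5.1 keeps the same two periods, the second being "Occurrence after the hospitalization period (from EoH to month 4", but omits the attribution sentence. Its own reason for the split is to check that late events are not lost among all events. Excess rate and NNT are compared between arms by period, for any TEAE and for preferred terms reaching 1% in one group.

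On exposure, SAP 1.1 reports "Tmax around 72h, stable for at least 4 days" and "Long half live (T1/2 of about 400h) allowing single administration". Protocol 1.3 refers to studies done as follows: "In the 13-week toxicity studies conducted to fully cover the length of time patients are exposed". Protocol 3.3 adds: "The visit at Month 4 corresponds to clearance of acoziborole as shown by results from the mass balance study". SAP 3.4.4, on determining actual treatment, counts safety events in anyone with detectable drug as acoziborole events and gives the long half-life as the reason.

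Protocol 3.3 bases the 5-day hospital stay on the pivotal study, where 97.7% of related TEAEs occurred within 5 days of dosing.

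**The concern.** Discharge is at Day 5, with an allowance to Day 8 (Protocol Table 2). On the quoted PK, a Day 5 discharge falls on or close to the concentration plateau. The late period therefore contains most of the exposure, yet the protocol says in advance that events there may be due to disease or may be persistent. SAP 3.4.4 leans the other way for the same drug. The persistence label also fits poorly with the start-date rule, because an event that began in hospital and continues is counted only in the first period.

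The primary objective is safety over 4 months. If a drug effect arises in the first few weeks after discharge, a 116-day window adds background events from the following three months to both arms. The excess is still estimated without bias, but less precisely. That matters most for the preferred-term and severity tables, where no other planned output isolates those weeks.

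**Working it through.** **The plan's own figures.** Month 4 is Day 121, so 120 × 24 = 2,880 h after dosing. That is 2,880/400 = 7.2 half-lives, leaving 0.5^7.2 = 0.7%. This agrees with the protocol's statement on clearance at Month 4. The 97.7% figure comes with no counts and cannot be recomputed. The documents give no exposure share by period.

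**Exposure shares.** Inputs are Tmax 72 h, half-life 400 h (ke = ln2/400 = 0.00173/h), Day 5 = 96 h, Day 8 = 168 h and Month 1 = 720 h. The curve shape is an assumption, so several were tried.

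- *First-order absorption.* ka is set so that ln(ka/ke)/(ka − ke) = 72, giving ka = 0.0478/h. Share of AUC after t = [ka·exp(−ke·t) − ke·exp(−ka·t)]/(ka − ke).
- *Linear rise to 72 h, plateau to 168 h, then decay.* Total = 36 + 96 + 400/ln2 = 709.1 units. AUC to 96 h = 36 + 24 = 60, so 60/709.1 = 8.5% has accrued.
- *Linear rise to 72 h, then decay with no plateau*, and *bolus* as a lower bound that ignores Tmax.

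| Shape (half-life 400 h) | After Day 5 | After Day 8 | Day 5 to Month 1 | After Month 1 |
|---|---|---|---|---|
| First-order | 88% | 78% | 58% | 30% |
| Plateau | 92% | 81% | 60% | 31% |
| Linear rise, no plateau | 90% | 80% | 60% | 31% |
| Bolus | 85% | 75% | – | – |

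Varying the half-life over 300 to 500 h in the first-order model gives 85 to 90% after Day 5 and 72 to 81% after Day 8. With a 400 h half-life, the modelled concentration is 98% of peak at 96 h, 66% at two weeks, 34% at Month 1 and under 1% at Month 4.

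**Effect on power.** The documents give no late background rate or effect pattern, so both are assumed. Take 900 against 300 subjects, two-sided 5%, constant background hazard and no attrition. The background over Days 6 to 31 is 1 − (1 − B)^(26/116); for B = 5% it is 1.14%. Power = Φ[(d − 1.96·se0)/se1], with se0 = √[p̄(1 − p̄)(1/300 + 1/900)] and se1 = √[p0(1 − p0)/300 + p1(1 − p1)/900].

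For B = 5% and a 3-point excess:

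- Pooled window, 5% against 8%: se0 = 0.0173, se1 = 0.0155, z = (0.030 − 0.0339)/0.0155 = −0.25, power 40%.
- Days 6 to 31, excess confined there, 1.14% against 4.14%: se0 = 0.0121, se1 = 0.0090, z = (0.030 − 0.0236)/0.0090 = 0.70, power 76%.

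If the excess follows AUC, two-thirds of it (about 60/90) falls in Days 6 to 31, which is 2 points. If it is uniform over the late period, 26/116 of it does, which is 0.67 points.

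| Late background, total excess | Pooled late window | D6–31, excess confined | D6–31, excess follows AUC | D6–31, excess uniform |
|---|---|---|---|---|
| 5%, 3 points | 40% | 76% | 45% | 10% |
| 10%, 3 points | 27% | 59% | 32% | 8% |
| 20%, 5 points | 42% | 80% | 48% | 10% |

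If the added risk acts independently of the background instead of adding to it, the first row's pooled and confined figures become 37% and 75%. On that same basis, the whole 4-month analysis has 36% power against 37% in the late window.

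**The case against.** A reader might infer that late drug effects will be passed off as disease. The documents do not support that. Each period is compared with randomised placebo, which carries the same disease background, so disease alone does not explain a systematic late excess over placebo. The attribution sentence is hedged, it is missing from the SAP, and Protocol 10 refers to the SAP for full statistical detail.

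Three further limits stand. The discharge split itself costs no power against the 4-month analysis; the loss comes from leaving the late window undivided. Month 1 does not separate exposed from unexposed time, since about 30% of AUC lies beyond it. Disease is also a real possibility: Protocol 1.6 says a variable proportion of suspects prove to be cases, and the plan allows for up to 20 to 25% dermal carriage.

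The two-period choice has an empirical basis in the 97.7% figure, and exposure share does not show when risk arises. That figure, however, counts only events judged related in an open-label study, where timing may have influenced the judgement. It is a finding for this blinded trial to test.

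The SAP also looks at Month 1 elsewhere: laboratory changes (5.2.3), vital signs (5.2.4), signs and symptoms (5.2.8), and Kaplan-Meier curves. None of these gives TEAE excess by preferred term or severity for the weeks after discharge. The log-rank test is a weaker safeguard than it appears, because SAP 5.1 stratifies it by site and treatment group. Taken literally, that cannot compare the arms.

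**Conclusion.** The point holds as a matter of interpretation and resolution, not bias. About 85 to 92% of exposure follows a Day 5 discharge and about 80% a Day 8 discharge, given a 400 h half-life and simple assumed curve shapes. The protocol's default reading of late events conflicts with that PK and with SAP 3.4.4, and the passages need reconciling.

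The benefit of a finer window depends on an unknown hazard. In the 5% background, 3-point case, power rises from about 40% to 76% if the excess is confined to Days 6 to 31, gains only about 5 points if it tracks AUC, and falls to 10% if it is uniform. These figures illustrate the range and do not predict what the trial will find. They justify adding a sub-period, but not replacing the pooled late window.

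**What to change.** In Protocol 10.7.1 and SAP 5.1, keep the two periods and divide the late one at Day 31, the nominal Month 1 visit, by AE start date. Give the same excess-rate, NNT, severity and preferred-term tables for each part, and name a denominator for each, for example by extending the present late-period rule. Delete the clause that attributes early events to treatment and late events to disease or persistence. State that interpretation in every period rests on the acoziborole-placebo excess.

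The visit and the AE start dates already exist, so the cost is SAP wording and one extra table block. The downside is one more set of unadjusted comparisons, which the plan already accepts for safety signals. Because the pooled late window stays, nothing is lost if the excess turns out to be spread evenly.
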